### *How will we do the work?*

Following ascertainment of eligibility, potential participants will be sent a letter inviting them to learn more about the study. Individuals who contact the study personnel in response to the letter will be screened on the phone and those who meet the inclusion criteria will be invited to come to the research center to be screened in person. At that time the study will be reviewed in detail and informed consent will be obtained. If an HgbA1c has not been measured in the previous month, a sample will be collected for this measure during the screening visit. Subjects will then be scheduled for their first study day and instructed to avoid exercise 48 hours before the study. Directions for how to manage their diabetes medications will be given to the participant. These will be individualized based on the participant's current regimen with the intention to discontinue all medications so none are present at the start of the study.

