Subjects will be admitted to Masonic Clinical Research Unit (MCRU) after dinner on the night (between 8-10 PM) before the study. Two catheters will be placed in the arms to establish intravenous access. One will be used for subsequent blood sampling and the other will be used for infusion. Blood glucose will be measured four hours after their dinner and intravenous insulin will be given as necessary to maintain blood glucose between 100-150 mg/dL. Blood sugars will be obtained every 15-60 minutes overnight to ensure the participant remains at target. At 7 AM (time 0) subjects will be given a blinded dose of either 100 or 200 units of U-500 regular insulin subcutaneously. The randomization to dose and the preparation of the injection will be managed by the investigational pharmacy. Blood glucose will be measured starting at time 0 and every 15-60 minutes and variable infusion of 20% dextrose (D20) will be used to maintain euglycemia (100 mg/dL target) according to pre calibrated algorithm. Samples for subsequent measurement of total insulin and c-peptide by Chemiluminescent immunoassay will be collected at time 0 and every 60 minutes. Measurements will be continued until the subject can maintain euglycemia without a glucose infusion for at least 10 hours or until the subject experiences hyperglycemia (BG > 150 mg/dL) for two hours after discontinuation of the glucose infusion irrespective of total duration of glucose infusion. At that point, the catheters will be removed and the subject will be discharged to home. In case of unusual circumstances including high requirements of glucose beyond 24 hours etc, we will assess for recent insulin dosing (< 15 hours as oppose to > 15 hours required per protocol), sulfonylurea screen etc. Carbohydrate free meals will be provided to the participant starting at noon and continued at traditional mealtimes thereafter for the duration of the glucose infusion. Non-caloric decaffeinated beverages will be available as needed. Subjects will be given their home dose of insulin prior to discharge.

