*What is the schedule of events?*

Please see figure 1. In random order subjects will be assigned to receive 100 or 200 units of U-500 insulin on two separate occasions separated by a minimum of two weeks. Following U500 administration, euglycemia will be maintained by the variable infusion of dextrose.

• **Concomitant medications**

Subjects will be continued on their non-diabetic medications. Medications used to treat diabetes will be discontinued before the study day. How medications will be discontinued will be individualized based on the participant's current regimen with the intention to discontinue all medications so none are present at the start of

the study. For example, individuals on metformin, sulfonylureas, DPP4Is, GLP-1 agonists will be instructed to not take this drug on the day they will be admitted to the research center.

- **Outcome measures**

**Primary outcome measure:** Duration (in hours) of 20 % dextrose infusion requirement.

**Secondary outcome measure:** 1) Peak 20 % dextrose requirement. 2) Area under the curve (AUC) of 20 % dextrose.

- **Safety measures**

**Investigator related measures:** Our research group has had extensive experience in subject recruitment of patients with diabetes in research studies including GRADE, ACCORD and REWIND. We have performed hundreds of precise clamp studies including euglycemic, hypoglycemic and hyperglycemic. We have a dedicated staff and are well equipped to handle these experiments.

**Subject related measures:** Subjects will be under constant supervision by staff of MCRU overnight during insulin infusion to keep blood glucose within target. U-500 insulin will be handled by Investigational Drug Service (IDS) pharmacy according to institutional policies regarding U-500 regular insulin (attached document: U 500 Insulin Safety Plan, U 500 insulin formulary committee meeting). Pre specified dose of U 500 regular insulin will be calculated, drawn and verified in U-100 insulin syringe at IDS pharmacy according to a conversion chart (attached document: U-500 regular insulin conversion chart). After the administration of insulin, the D20 infusion will be titrated by an experienced member of the group. Subject will remain in the research unit until the subject can maintain euglycemia without a glucose infusion for at least 10 hours or until the subject experiences hyperglycemia (BG > 150 mg/dl) for two hours after discontinuation of the glucose infusion.

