## Important Safety Information for Humulin R U-500, continued

### Precautions, continued

- **Hyperglycemia, Diabetic Ketoacidosis, and Hyperosmolar Non-Ketotic Syndrome:** Hyperglycemia, diabetic ketoacidosis, or hyperosmolar coma may develop if the patient takes less Humulin R U-500 than needed to control blood glucose levels. Severe sustained hyperglycemia may result in hyperosmolar coma or death.
- **Hypokalemia:** Insulin use can lead to hypokalemia, that left untreated may cause respiratory paralysis, ventricular arrhythmia, and death. Use caution in patients who may be at risk for hypokalemia (eg, patients using potassium-lowering medications, patients taking medications sensitive to serum potassium concentrations).
- **Hypersensitivity and Allergic Reactions:** Severe, life-threatening, generalized allergy, including anaphylaxis, can occur with insulin products, including Humulin R U-500. Localized reactions and generalized myalgias have been reported.
- **Renal or Hepatic Impairment:** Frequent glucose monitoring and insulin dose reduction may be required.
- **Drug Interactions:** Some medications may alter insulin requirements and the risk for hypoglycemia and hyperglycemia. Some medications may mask the signs of hypoglycemia in some patients. Therefore, insulin dose adjustment and particularly close monitoring may be required.
- **Pregnancy Category B:** There are no adequate and well-controlled clinical studies of the use of Humulin R U-500 in pregnant or nursing women or during labor and delivery.
- **Pediatric Use:** There are no well-controlled studies of use of Humulin R U-500 in children.

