#### Hypokalemia

Insulin stimulates potassium movement into the cells, possibly leading to hypokalemia, that left untreated may cause respiratory paralysis, ventricular arrhythmia, and death. Use caution in patients who may be at risk for hypokalemia (e.g., patients using potassium-lowering medications, patients taking medications sensitive to serum potassium concentrations).

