• lightheadedness	• abnormal behavior
• trouble concentrating	• walking unsteady
• headache	• personality changes

Humulin R U-500 can cause low blood sugar (hypoglycemia) that is severe and that can last a long time.

0. • Severe low blood sugar can cause you to become confused, pass out (become unconscious), have seizures or coma, and could cause death.

Talk to your healthcare provider about how to tell if you have low blood sugar and what to do if this happens while taking

Humulin R U-500. Know your symptoms of low blood sugar. Follow your healthcare provider's instructions for treating your low blood sugar.

Tell your healthcare provider if low blood sugar is a problem for you. Your healthcare provider may need to change the amount of Humulin R U-500 that you take, change your meal plans or your exercise program to help you avoid low blood sugar.

- • Serious allergic reactions. Get medical help right away if you have any of these symptoms of a severe allergic reaction:

- • rash all over your body
- • shortness of breath
- • trouble breathing (wheezing)
- • fast heart beat
- • sweating
- • feel faint
- • Low potassium (hypokalemia) in your blood. Your healthcare provider may do blood tests to check you for low potassium.

Common side effects of Humulin R U-500 include:

- 0. • Skin thickening or pits at the injection site (lipodystrophy). Change (rotate) where you inject your insulin to help prevent these skin changes from happening. Do not inject insulin into this type of skin. Do not inject into the exact same spot for each injection.

HUMULIN® R REGULAR U-500 (CONCENTRATED)

INSULIN HUMAN INJECTION, USP (rDNA ORIGIN)

PA 8902 AMP

- 0. • Injection site reactions (local allergic reaction). Symptoms may include: redness, swelling and itching at the injection site. Tell your healthcare provider if you have skin reactions that do not go away.

Humulin R U-500 may cause serious side effects, including:

- • swelling of your hands and feet
- • heart failure. Taking certain diabetes pills called thiazolidinediones or "TZDs" with Humulin R U-500 may cause heart failure in some people. This can happen even if you have never had heart failure or heart problems before. If you already have heart failure it may get worse while you take TZDs with Humulin R U-500. Your healthcare provider should monitor you closely while you are taking TZDs with Humulin R U-500. Tell your healthcare provider if you have any new or worse symptoms of heart failure including:

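### The readable protocol names no potassium test at screening or at either U-500 clamp visit, although non-diabetic drugs continue and the attached label advises caution about hypokalemia

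*Combined protocol and SAP*

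**What the plan says.** Screening, under How will we do the work?, names one laboratory test: "If an HgbA1c has not been measured in the previous month, a sample will be collected for this measure during the screening visit". The inclusion and exclusion criteria contain no potassium limit and no restriction on drugs that lower potassium.

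On the night before each dose, "intravenous insulin will be given as necessary to maintain blood glucose between 100-150 mg/dL", and "Blood sugars will be obtained every 15-60 minutes overnight to ensure the participant remains at target". From the 7 AM injection, the named measurements are glucose every 15 to 60 minutes and hourly samples for total insulin and C-peptide. For unusual cases the protocol adds a check on recent insulin dosing and a sulfonylurea screen, and leaves that list open. The second visit repeats the first visit's sampling.

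Concomitant medications states: "Subjects will be continued on their non-diabetic medications". The subject-related safety measures cover supervision, the glucose target, pharmacy handling, dextrose titration and the rule for leaving the unit.

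The attached safety information for U-500 says: "Insulin use can lead to hypokalemia, that left untreated may cause respiratory paralysis, ventricular arrhythmia, and death". The label's Hypokalemia paragraph says "Use caution in patients who may be at risk for hypokalemia", and the examples given are "patients using potassium-lowering medications, patients taking medications sensitive to serum potassium concentrations". The patient leaflet says "Your healthcare provider may do blood tests to check you for low potassium".

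**The concern.** The label that the protocol attaches names a hazard and describes who is most exposed to it. The protocol keeps those people on their drugs, does not identify them, and plans no measurement that would detect the hazard.

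Three features of the design make this more than a general remark about insulin:

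- **Dose.** Eligibility starts at 100 units of insulin per day, so for a participant at that minimum the 200-unit injection is 200/100 = 2 times the usual daily total, given at once.
- **Earlier insulin.** Intravenous insulin may already have been given overnight.
- **Clamped glucose.** Dextrose holds glucose near 100 mg/dL, so the quantity that staff watch most closely says nothing about potassium.

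At stake is participant safety. The statistical comparison of the two doses is not affected.

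**Working it through.** The plan states no figure on this point, so there is none to reproduce. The check sets the planned tests beside the label's caution and then counts the assays a remedy would need.

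**Tests named at each stage**

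| Stage | Tests named in the readable text | Potassium |
|---|---|---|
| Screening | HbA1c, if none in the previous month | No |
| Eligibility criteria | HbA1c range | No |
| Night before the dose | Blood glucose | No |
| Clamp, visit 1 | Glucose; hourly insulin and C-peptide | No |
| Unusual cases | Recent insulin dosing; sulfonylurea screen; list left open | Not named |
| Clamp, visit 2 | As visit 1 | No |
| Subject-related safety measures | Glucose target only | No |

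The institutional U-500 safety plan, formulary note and dosing guidelines deal with dosing and handling, not potassium. Potassium testing appears only in the patient leaflet, which is general product text and not a study procedure. The label's overdosage section calls for hypokalemia to be corrected, which presupposes that someone has found it.

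**Visits.** 15 participants x 2 doses = 30 completed visits. Potassium tests named: 0.

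**Time for a pre-dose result.** Admission is between 8 and 10 PM and the dose is at 7 AM. That leaves 11 hours (8 PM to 7 AM) or 9 hours (10 PM to 7 AM), with a sampling catheter in place and glucose already being drawn.

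**Assay counts**

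- Pre-dose only: 30 visits x 1 = 30.
- Upper case, in which every participant is also retested while dextrose runs. Tests per visit = floor(infusion hours / interval) + 1, where the 1 is the pre-dose test.
- Infusion time is an assumption: 10 hours at the low end and 24 hours at the high end. The label gives action of up to 24 hours, and the protocol treats a high glucose requirement beyond 24 hours as unusual.
- Low: every 6 hours over 10 hours = floor(1.67) + 1 = 2 per visit; 2 x 30 = 60.
- High: every 4 hours over 24 hours = floor(6) + 1 = 7 per visit; 7 x 30 = 210.

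Each participant who does not return and is replaced adds one first visit: 1 assay, or 2 to 7 in the upper case. An infusion longer than 24 hours adds more.

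**The case against.** The strongest reply is that no requirement is missed. The label asks for caution in patients at risk, and the leaflet says only that a provider may test. Moving from caution to a fixed testing schedule for everyone is clinical judgement, and no document supports any particular interval. This stands, and it limits the remedy: serial testing of all participants is not justified by these documents.

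The second reply is that the risk is already reduced. Current organ failure, vascular disease and recent systemic corticosteroid use are exclusions, and age is capped at 65. Participants are supervised as inpatients with intravenous access, by a team with long clamp experience, and staff may test on clinical grounds. This also stands, and it bears on how serious the gap is. It does not close the gap: overnight supervision is described in terms of glucose, the exclusions do not cover users of potassium-lowering drugs, and nothing in the text prompts a test.

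The third reply is that the schedule of events points to Figure 1, which is not shown. Its caption says only that it shows the study design, so it may list no laboratory tests, but that cannot be confirmed. The point therefore holds for the readable text, with medium confidence.

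A reader might also infer that a known share of participants is in danger. The documents give no rate of hypokalemia and no count of participants on relevant drugs, so no such figure can be stated.

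**Conclusion.** The point holds as a gap that should be closed. In the readable text, the plan gives 100 or 200 units of U-500, possibly after overnight intravenous insulin, at 30 completed visits with no potassium test named, while non-diabetic drugs continue without exception and the attached label advises caution for some of their users.

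A reader might go further and conclude that the protocol violates the label or omits mandatory monitoring. The documents do not support that, because the label sets no testing requirement.

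The conclusion rests on two conditions: that Figure 1 does not schedule a potassium test, and that no unit procedure outside these documents does so. If either does, a one-line cross-reference settles the matter. The absence of a named test needs no assumption about infusion time. Only the upper range of the cost does.

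**What to change.** **Before each dose.** In How will we do the work?, add one serum potassium at each visit, drawn from the existing catheter overnight and early enough to be read before 7 AM. If the value is below the unit's lower limit, hold the dose and replace potassium in a dextrose-free fluid. If it is not corrected in time, reschedule.

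**During the clamp.** Identify users of potassium-lowering or potassium-sensitive drugs at record review, or at the screening visit for referred participants. While dextrose runs, repeat potassium from the existing hourly draws for these participants, for anyone with a low-normal pre-dose value, and for anyone on clinical grounds. The investigator sets the interval, for example every 4 to 6 hours. These samples must be run promptly and not held for later assay with insulin and C-peptide. Any replacement should again be dextrose-free, so that the dextrose outcomes are not altered. The protocol provides one sampling and one infusion catheter, so the wording should say how a replacement fluid would be given alongside the dextrose.

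**Cost.** Protocol wording and at least 30 assays over 30 completed visits. The total would reach 60 to 210 only if every participant were retested, under the infusion times assumed above. A low pre-dose value may occasionally mean a rescheduled visit, with another 15-hour medication washout and overnight admission, and may strain the two-to-four-week window between visits. Sample size, alpha, power and outcomes are unchanged.

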### *What is our study population?*

We will study adults with type 2 diabetes and insulin resistance. Criteria for participation are listed below.

- **Inclusion Criteria**
  - Type 2 diabetes
  - Ages 30-65 years
  - A1c between 7-9.5% within the past month
  - On  $\geq$ 100 units of insulin per day.

- Willing to discontinue oral/injectable non-insulin or insulin hypoglycemic agents for minimum of 15 hours prior to the expected U-500 dose administration.
- Willing to avoid exercise 48 hours prior to study
- Willing to be fasting for up to 24 hours
- BMI between 27 and 38 kg/m^2
- **Exclusion criteria**
  - On systemic corticosteroids in preceding 3 months
  - Heavy alcohol consumption (>21 drinks/week men, >14 drinks/week women)
  - Unwillingness to stop alcohol consumption for 24 hours before each study visit
  - Pregnant or actively trying to conceive
  - Current diagnosis of active infection, cancer (other than basal cell carcinoma), vascular disease, organ failure
  - Current transplant recipient

*How are subjects being selected into the study?*

Potential participants will be recruited from the Diabetes Clinics at the University of Minnesota. They will initially be ascertained for eligibility by review of the electronic medical record or on referral by their personal health care provider.

*What are your treatment groups?*

Each individual will be studied twice, once after the administration of 100 units of U 500 and once after the administration of 200 units of U500. Dosage administration will be in random order.

*What is our assignment strategy?*

The investigational pharmacy at the University of Minnesota will dispense the doses of U 500 insulin and assign the order of administration based on a randomization scheme developed by [name], the biostatistician on the project.

*How many subjects per treatment group?*

We have powered the primary research question using 15 participants, each studied twice as described above. A participant who completes the first dose study but does not return for the second dose study will be replaced.

With 15 subjects (N = 15) completing this cross over study design, we have 85% power using a paired t-test to detect at least a 2 hour difference in the mean duration of action of the 100 vs 200 unit dose of U500 conservatively assuming a within-person correlation of 0.30 (Figure 2). Power will be higher (the detectable difference will be smaller) if the within-person correlation is larger.

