## U-500 Insulin Safety Plan

**Situation:** Non-standard insulin concentrations (eg. U-500) are high risk medications that require additional safety measures to prevent errors.

**Background:** Insulin products are typically prescribed using a concentration of U-100 (100 units/mL). Increasingly we are seeing requests for non-standard concentrations, particularly for the commercially available U-500 (500 units/mL) regular insulin. This product can be difficult to order, prepare and administer. An error with this high risk medication could have significant adverse events associated with the administration and result in severe, prolonged hypoglycemia.

U-500 regular insulin is typically used in patients that have a high resistance to insulin, most often in patient that require >100 units/dose. This insulin is usually administered on a q8h schedule (NOT PRN).

In the outpatient setting, patients are thought to use an insulin syringe to draw doses. Because of this, the nomenclature patients learn are usually both the actual dose of insulin they are to administer in actual units of insulin, as well as what mark on an insulin syringe to draw the dose up to. Example: 100 units of U-500 insulin = 20 units on an insulin syringe. This can be very confusing not only to patients, but to others providing care.

Our current safety practices for U-500 insulin:

Specific entry in Epic for U-500. Currently this requires both the actual Units of U-500 to be administered as well as the volume in mL to which it is to be drawn.

Storage in central pharmacy is in the C-II safe, away from all other insulin products  
Pharmacy must draw up individual doses

**Assessment:** Several aspects of our safety plan could be improved in addition to our current practices. These include:

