### Formulary

- o Restrict to use only when each dose is >100 units
- o Implement pharmacy consult for **all** U-500 patients
  - Double check patient's home dose and make sure ordered correctly
  - Autosub any doses </= 100 units to regular U-100 insulin

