### Ordering

- o BPA to fire for providers if dose is <101 units not allowing them to process order
- 0 . o Revise Epic ordering so that mLs is not part of the order as it leads to confusion because insulin syringe is not in mL
- 0 . o Attach a document to the order with a crosswalk of actual dose to units on an insulin syringe

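### Do the attached U-500 pharmacy policies rule out the 100-unit study dose?

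*Combined protocol and SAP*

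**What the plan says.** The treatment-groups section has each participant studied twice, "once after the administration of 100 units of U 500 and once after the administration of 200 units of U500". The Objectives and Research design sections name the same product and the same two doses.

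Under Safety measures (Subject related measures), the protocol says "U-500 insulin will be handled by Investigational Drug Service (IDS) pharmacy according to institutional policies regarding U-500 regular insulin". It names two attachments at that point: the U-500 Insulin Safety Plan and the formulary committee document. The next sentence says "Pre specified dose of U 500 regular insulin will be calculated, drawn and verified in U-100 insulin syringe at IDS pharmacy", using an attached conversion chart.

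The Safety Plan includes these items:

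- Formulary: "Restrict to use only when each dose is >100 units" and "Autosub any doses </= 100 units to regular U-100 insulin".
- Ordering: "BPA to fire for providers if dose is <101 units not allowing them to process order".

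These come after an Assessment that opens "Several aspects of our safety plan could be improved in addition to our current practices". The closing Plan paragraph asks for approval at a meeting on 10/31/12, seeks formulary approval for the restrictions, and aims for roll-out by 12/1/12. The May 2008 formulary committee document suggests, if it can be built, an order rule that prohibits U-500 only below 100 units.

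**The concern.** The protocol appears to adopt, as the handling rule for study drug, a document that excludes one of its own two doses. It states no exemption for study doses, no order of precedence between the two attachments, and no policy version in force. The Safety Plan's roll-out target precedes the protocol version of September 23, 2015 by about 34 months, and nothing records whether the plan was approved in between.

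The stake would be the primary contrast. If the 100-unit dose were dispensed as U-100, the trial would compare 100 units of U-100 with 200 units of U-500, so dose and concentration would change together. The attached prescribing information (Clinical Pharmacology) attributes the long action of U-500 to its high concentration, and duration is the primary outcome. If the order were blocked instead, the 100-unit visit could not go ahead as written.

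**Working it through.** There is no planned statistical figure to reproduce. The check applies each written threshold to the two study doses and then asks what standing each threshold has.

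**Thresholds against doses**

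| Source | Rule on U-500 | 100 units | 200 units |
|---|---|---|---|
| Safety Plan, Formulary | allowed only above 100 | excluded | allowed |
| Safety Plan, Formulary | 100 or less switched to U-100 | switched | not switched |
| Safety Plan, Ordering | order blocked below 101 | blocked | not blocked |
| May 2008 committee | prohibited below 100 | not prohibited | not prohibited |

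For whole-unit doses, the three Safety Plan lines are one cutoff written three ways, so they do not count as three separate conflicts. Over whole-unit doses from 1 to 500, the Safety Plan and the 2008 suggestion disagree at one value only, 100 units. The literal mismatch is therefore confirmed.

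**Volumes**

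- 100 units of U-500: 100 / 500 = 0.2 mL, and 100 / 5 = 20 syringe markings.
- 200 units of U-500: 200 / 500 = 0.4 mL, and 200 / 5 = 40 markings.
- 100 units if switched to U-100: 100 / 100 = 1.0 mL, and 1.0 / 0.2 = 5 times the planned volume.

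The first two results match the attached conversion chart.

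**Exposure**

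15 participants × 2 visits = 30 planned injections, of which 15 are at 100 units. The number affected is 15 if the cutoff applies to every study dose and 0 if it does not apply.

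**Standing of the thresholds**

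1. The Safety Plan lists its current practices as a dedicated electronic order entry, storage in the secure safe, and pharmacy preparation of individual doses. None contains a dose threshold.
2. The cutoff appears only in the list of possible improvements, and the Plan paragraph is still asking for approval.
3. The 2008 item is a recommendation, made conditional on being feasible in the ordering system of the time. Two proposals about four years apart that differ at the boundary are not two operating rules in conflict.
4. The Safety Plan's own Background uses the study dose as its illustration: "Example: 100 units of U-500 insulin = 20 units on an insulin syringe".
5. The Formulary and Ordering items concern a check of the patient's home dose and an alert to prescribers. The protocol places randomization and syringe preparation with the investigational pharmacy. The parts of the attachments that fit the handling of study drug most naturally are storage, drawing to dose and the double check.

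**The case for a change.** The strongest case for a change is that the protocol cites the Safety Plan as governing policy, whatever that document's history. If the cutoff is in force, it excludes a study dose. If it is not, the protocol relies on unadopted proposals as part of its safety control. Either way a sentence seems to be missing. The substitution item also cannot be set aside as a prescriber alert, because it sits under a pharmacy consult for all U-500 patients and the protocol gives study drug to a pharmacy. The Safety Plan treats non-standard concentrations as high risk, and clarification would cost a sentence or two.

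Part of this stands. The cited text and the 100-unit dose do not agree as written, no exemption is stated, and the documents do not show what was in force in September 2015. What does not follow is any effect on the trial. The sentence straight after the policy citation tells the same pharmacy to draw the pre-specified dose as U-500, and the chart it must use has a row for 100 units. Substituting U-100 would breach that specific instruction. A risk to blinding from unequal volumes adds little, since the planned doses already differ (0.2 against 0.4 mL). A sentence naming the policy version, or a log field for product and concentration, would be tidy but would not alter the design, the data or the analysis.

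**Conclusion.** The mismatch is confirmed as a matter of wording: one cutoff in a cited attachment, read literally, catches exactly one of the two study doses. No change to the plan follows. The protocol's specific dosing and preparation text settles which product is to be dispensed, and followed as written it delivers 100 against 200 units of U-500. How the general policy citation and the attachment's cutoff are to be reconciled for study doses is a detail that the study pharmacy and the investigator can be expected to settle in ordinary set-up.

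The effect shown from the documents is nil. The conditional range of 0 to 15 of 30 injections spans every possible outcome for the 100-unit visits, so it says nothing about likelihood. The 85% power statement for 15 participants and the paired comparison are untouched.

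This rests on two assumptions: that the study pharmacy follows the explicit preparation instruction, and that the proposed cutoff was either not in force or not applied to study doses. The documents support the first directly. On the second they are silent beyond presenting the cutoff as a proposal. Confidence is high on the wording and low on any claim that dosing was at risk. No view is taken on which dose or threshold is right.
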